#### *Variability in response to suvorexant treatment*

We will determine whether the effect of suvorexant are modified by the following patient, procedure, and anesthesia-related factors: subjective TST during the nights prior to surgery measured by RCSQ, , cardiovascular function impairment (norepinephrine equivalent dose), duration of mechanical ventilation, total propofol dose since skin incision, and markers of pain intensity such as total opioid dose since skin incision for up to 48 hours postoperatively and numeric rating scale (NRS) pain scores (scale from 0 [no pain] to 10 [worst pain]) [23] obtained by nursing staff blinded to treatment allocation on each evening before study drug administration for 7 days. To account for surgical complexity as a marker of postoperative stress response, we will further include duration of bypass time, total blood loss, and the Procedural Severity Score for mortality (PSS mortality).

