## B3. DESCRIPTION OF RESEARCH PROTOCOL

### A. Study Design – Overview, Methods, Procedures

#### Study design & overview

- This is a single-center, randomized, double-blind, placebo-controlled trial expected to enroll 120 subjects. Participants will be enrolled preoperatively and randomized in a 1:1 ratio to receive suvorexant or placebo. Prior to randomization, informed consent will be obtained from all participants. The patient is first asked to report information about their sleep using the Richards-Campbell Sleep Questionnaire (RCSQ). Patients will be asked to complete a sleep questionnaire for at least one night before surgery or, if possible, daily, starting 3 days before surgery. The questionnaire will be performed online in RedCap; patients will be emailed a link to the survey. If patients do not have access to an internet-enabled device, they will be handed the RCSQ on paper and asked to complete it before surgery. The intervention (study drug) will be applied for 7 nights starting the night after postoperative extubation in the ICU. Primary and secondary outcomes will be assessed once during the night of the sleep trial in the ICU. The sleep trial will take place during the first night after extubation if the patient has been extubated before 7pm. If patient is extubated after 7:00 pm study medication will be administered the night after extubation only if still in ICU.

Exploratory outcomes will be assessed from day of extubation until hospital discharge. An outline of the study procedures is provided in **Figure 2**.

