#### Study interventions

Suvorexant 20 mg or placebo will be administered p.o. once a day at 9:00 pm for a maximum of 7 days starting the night after extubation in the ICU. A one-hour window (9:00 pm-10:00 pm) to administer the drug will ensure protocol adherence in case of delays in drug administration. Prior to every study drug administration, the Richmond Agitation-Sedation Scale will be assessed. In case of RASS < -1, the study drug will not be administered on that same day. The study drug will be discontinued:

1. After 7 consecutive doses following extubation; or

2. At hospital discharge (if less than 7 days after extubation); or
3. At ICU discharge, if patient showed signs of airway obstruction during sleep; or
4. At ICU discharge or after a maximum of 3 consecutive doses, whichever occurs sooner, if strong inhibitors of CYP3A (e.g. digoxin, diltiazem, verapamil) are co-administered; or
5. In the event of early termination: subject withdraw of consent, investigator withdrawal for toxicity or other reasons.

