#### *Variability in response to suvorexant treatment*

To determine whether there is an association between each of the previously described potential confounders and TST during the night of the sleep trial, we will use logistic regression models. Subsequently, we will evaluate a potential interaction between any statistically significant predictor of TST and suvorexant treatment on total sleep time.

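### Two candidate effect modifiers, opioid dose to 48 hours and evening pain scores over 7 days, are collected past the first study dose and often past the only night on which TST is measured

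*Combined protocol and SAP*

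**What the plan says.** Section B3 uses the heading Variability in response to suvorexant treatment twice.

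- **Under Assessment of study endpoints**, it lists the factors whose modification of the drug effect will be examined. Two of them are "total opioid dose since skin incision for up to 48 hours postoperatively and numeric rating scale (NRS) pain scores". The pain scores are obtained "on each evening before study drug administration for 7 days".
- **Under Exploratory analyses**, each factor is first tested for association with TST on the sleep-trial night. Then: "Subsequently, we will evaluate a potential interaction between any statistically significant predictor of TST and suvorexant treatment on total sleep time".

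The timing comes from other parts of B3.

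- Study interventions: "Suvorexant 20 mg or placebo will be administered p.o. once a day at 9:00 pm for a maximum of 7 days". The first of these doses falls on the night that follows extubation.
- Study design & overview: "Primary and secondary outcomes will be assessed once during the night of the sleep trial in the ICU". Also: "The sleep trial will take place during the first night after extubation if the patient has been extubated before 7pm". For later extubations: "If patient is extubated after 7:00 pm study medication will be administered the night after extubation only if still in ICU".
- Assessment of study endpoints: the WASO observation period is 10 PM to 6 AM, and TST is measured by analogy.
- Rescue medications: opioids may be given for pain at the primary care team's discretion, with no restriction relative to the study dose.

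Nothing in the document ends the opioid window at the first study dose or says which pain score enters the model.

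**The concern.** An effect modifier has to be fixed before treatment can act on it. A variable measured later may have been changed by the treatment or, here, by the outcome. A patient who lies awake in pain may be given more opioid that night and report more pain the next evening. The drug itself may alter either one. An interaction between treatment and such a variable mixes modification with consequence and cannot be read as showing who responds to suvorexant.

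The two-step procedure adds to the problem. Only factors significantly associated with that night's TST go forward to the interaction test, so an association produced by poor sleep can carry a factor through the screen.

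At stake is the exploratory hypothesis that perioperative factors, including centrally acting drugs, modify the effect on sleep.

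**Working it through.** **Figures in the plan.** The plan gives no power or sample size for the modifier analysis. Its two stated power figures reproduce with an exact two-sample t-test at 50 per group: 91.0% for WASO (stated as above 90%) and 84.4% for delirium-free days (stated as 84.4%). Neither bears on this point.

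**Inputs from the document.** First dose at 9 pm (21:00); TST night over at 6 AM; opioid window ending 48 h postoperatively; up to 7 evening pain scores, each taken before that evening's dose; TST measured on one night.

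**Assumptions.** Surgery ends between 11:00 and 18:00. The sleep-trial night is the night of the first dose. The rule for extubation after 7 pm means a first dose the following evening. The seven pain evenings start with the first dosing evening.

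**Pain scores.** The first score precedes the first dose and is a true baseline. The other 7 − 1 = 6 follow both the first dose and the TST night: 6/7 = 86%. The number is smaller when treatment ends before seven days.

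**Opioid window by time.** Let h be the hours from end of surgery to first dose: h = 21 − (hour surgery ends) + 24 × (days from surgery to first dose). Hours after the dose are 48 − h. Hours after 6 AM are 48 − h − 9, since 21:00 to 06:00 is 9 h.

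| First dose | Surgery ends | h | Hours after dose | Hours after 6 AM |
|---|---|---|---|---|
| Evening of surgery | 11:00 | 10 | 38 (79%) | 29 (60%) |
| Evening of surgery | 18:00 | 3 | 45 (94%) | 36 (75%) |
| Next evening | 11:00 | 34 | 14 (29%) | 5 (10%) |
| Next evening | 18:00 | 27 | 21 (44%) | 12 (25%) |

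With a first dose two evenings after surgery, h is at least 51, so the whole window closes before the dose. The 18:00 case with a same-evening dose is extreme, because it needs extubation within an hour of surgery to meet the 7 pm limit.

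**Opioid window by dose.** The modifier is a total from skin incision, so intraoperative opioid counts. Let f be the intraoperative share of the total and assume even dosing over the 48 h. The share given after the first study dose is (1 − f)(48 − h)/48. For a first dose on the evening of surgery and surgery ending 11:00-16:00 (h from 10 to 5):

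- f = 0: 79-90%
- f = 0.25: 59-67%
- f = 0.50: 40-45%
- f = 0.75: 20-22%

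The document gives neither f nor the distribution of extubation times, so these are ranges and not estimates.

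**After the fix.** With both windows closed at the first dose, the post-dose share is 0% for each.

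**The case against.** The best defence is that the endpoint section lists what will be collected and does not specify model terms. Each pain score precedes that evening's dose, so the series contains a valid baseline, and the analysis section never says that all seven scores will be used. Dosing and delirium follow-up last for days, so a seven-day series could serve other outcomes. This stands in part for pain, where the fault is that no score is chosen. It does not rescue the opioid measure, whose 48-hour end is a stated rule. Nor does the plan describe a modifier analysis for any outcome other than TST on the one night.

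Three further objections hold and limit the claim.

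- A reader might infer that these two factors cannot be tested as modifiers at all. The document does not support that: the first-evening pain score and the opioid given before the first study dose are both pre-treatment and usable.
- A reader might infer that the opioid total lies mostly after the first dose. By time this holds for a dose on the evening of surgery. It fails for a next-evening dose, and by amount it can fail on either schedule if intraoperative use is large.
- Reverse causation is possible, but its size is unknown. Opioids may also affect sleep directly, as the background section notes, so whether these variables would pass the screen cannot be predicted.

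It is also fair to say that no distortion has been shown for propofol or norepinephrine. Propofol has a start and no stated end, and norepinephrine has no stated window. For these two the cut-off is a clarification.

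**Conclusion.** The defect is real but narrow. Followed as written, the plan puts post-treatment opioid data, and possibly post-treatment pain data, into an interaction test on a single night's TST. For pain, 6 of 7 scheduled scores follow that night. For opioids, the part of the 48 postoperative hours that follows the dose is 79-94% with a first dose on the evening of surgery, 29-44% with one the next evening and none with one two evenings later, given the assumed surgery end times. Because that part differs between patients, the same 48-hour total also combines pre-dose and post-dose exposure differently from one patient to the next.

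The bias is confined to an exploratory analysis. It would be wrong to infer that the WASO comparison, the main TST comparison or the sample size is affected; none of them uses these variables. It would also be wrong to extend the point to the initial duration of mechanical ventilation, which ends before randomisation. The change should be made, but the trial's main conclusion does not depend on it.

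**What to change.** Amend both places headed Variability in response to suvorexant treatment so that these modifiers use pre-dose values only:

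- opioid: cumulative dose from incision up to the first administration of study drug;
- pain: the single NRS score from the sleep-trial evening, taken before the first dose;
- propofol and norepinephrine equivalents: the same cut-off at the first dose.

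Report opioid given after the first dose, and pain on later evenings, descriptively by arm.

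The change is to the wording of the analysis plan, with no effect on sample size, procedures or care. It has two costs. The opioid total used as a modifier covers a shorter exposure. Administration times must also be extracted from the medication record: the endpoint section says that medications administered will be recorded but does not mention times.

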## **B. Statistical Considerations**

### **Sample Size Justification**

We will consider a 30 minute difference in WASO as clinically meaningful, with a standard deviation (SD) of 45 minutes [24]. Accordingly, we expect that a sample size of 50 subjects per group will provide us with >90% power to detect this difference between treatment groups, using a two-sample t-test with 2-sided  $\alpha=0.05$ . As for the exploratory outcome, we may see a difference of 3 delirium-free days (this assumption is based on findings observed with early mobilization by us in a similar cohort [25]) between groups with a SD of 5 days. The given sample size of a total of 100 patients will yield a power of 84.4% to detect a difference in the exploratory

outcome. To account for drop-out, we plan to enroll up to 120 patients to achieve our desired sample size of 100 completed participants.

### **Data Analysis**

The statistical analyses will be initiated by blinded study team members supervised by a BIDMC statistician. All study personnel will be blinded to the treatment group of the subject, except the investigational pharmacist. For the purpose of the final analysis, unblinding will be performed by the statistician and the research team. The research database will not be unblinded until the medical/scientific review has been completed, protocol violations have been identified (if appropriate), and data collection has been declared as complete.

All analyses will be conducted by research staff supervised by a BIDMC statistician and performed in Stata (StataCorp LP, version 13.0 or higher) and Rstudio (Rstudio.INC, Boston, MA, Version 1.1.4638). All personnel involved in data analyses will be blinded to intervention group assignment. A two-sided P value of <0.05 will be considered statistically significant.

#### Primary and secondary analyses

The primary and secondary analyses will be by intention-to-treat and will compare WASO and TST between patients receiving suvorexant or placebo. Baseline characteristics of the two groups will be presented descriptively. Normally distributed continuous variables will be expressed as means and standard deviations, non-normally distributed variables as medians and interquartile ranges, and categorical variables as frequencies and percentages. We will calculate the standardized differences of baseline characteristics between the two groups. To determine whether times of WASO and TST differ between treatment groups, we will analyze our data using a Student's t test, or Mann-Whitney-U test, as appropriate.

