#### Exploratory outcomes

*Time to sleep onset (TSO)* during the night of the sleep trial will be assessed using electroencephalography.

*Subjective sleep quality* will be assessed by applying the Richards-Campbell Sleep Questionnaire (RCSQ). The RCSQ is a validated survey instrument for assessing sleep quality in critically ill patients based on a five-item, visual analogue scale (each from 0 [worst value] to 100 [best value]) [8]. The scale evaluates perceptions of depth of sleep, sleep onset latency, number of awakenings, time spent awake, and overall sleep quality.

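### Preoperative RCSQ scores are collected before randomization but do not adjust the WASO or TST comparisons, and the RCSQ outcome has no specified comparison: lost efficiency of uncertain, probably modest size, not bias

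*Combined protocol and SAP*

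**What the plan says.** **Collection.** Under Study design & overview, patients are asked to "complete a sleep questionnaire for at least one night before surgery or, if possible, daily, starting 3 days before surgery". Under Randomization and blinding, allocation follows extubation and is stratified by perioperative anesthesia and sedation time at a cut-off of 420 minutes. The questionnaire is therefore a genuine pre-randomization measurement.

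**Main comparisons.** The section Primary and secondary analyses sets out to establish "whether times of WASO and TST differ between treatment groups, we will analyze our data using a" two-group test, which is either Student's t or Mann-Whitney U. No covariate is named, neither the baseline RCSQ nor the stratification factor. Time to sleep onset is handled in the same way under Exploratory analyses.

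**Where the baseline is used.** Under Variability in response to suvorexant treatment, the endpoint section lists "subjective TST during the nights prior to surgery measured by RCSQ" among the candidate effect modifiers. The analysis section of the same name says that, for the association between "each of the previously described potential confounders and TST during the night of the sleep trial, we will use logistic regression models", and that it will then "evaluate a potential interaction between any statistically significant predictor of TST and suvorexant treatment on total sleep time".

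**RCSQ as an outcome.** Under Exploratory outcomes, subjective sleep quality "will be assessed by applying the Richards-Campbell Sleep Questionnaire (RCSQ"). It is missing from the numbered list under Study endpoints. The analysis text, from Primary and secondary analyses through Multiplicity, gives it no test, model, summary score or time point.

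**The concern.** A measurement taken before randomization that predicts the outcome can be put into the treatment comparison to shrink its standard error without enrolling anyone else. The trial already collects such a candidate, and the plan itself treats preoperative sleep as a possible predictor of TST. Yet the comparisons of WASO and TST, where a predictor would improve precision, leave it out.

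The RCSQ outcome has a different gap. The same instrument is measured before randomization, so its baseline is the obvious covariate, but there is no planned comparison to which it could be added. If summary score, night and model are all chosen after unblinding, the result will carry little weight even as an exploratory finding.

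At stake are the width of the WASO and TST intervals and the credibility of the subjective sleep result.

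**Working it through.** **Inputs from Sample Size Justification:** WASO difference 30 min, SD 45 min, 50 completers per group, two-sided alpha 0.05, two-sample t test, stated power above 90%.

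**Input the documents do not give:** r, the correlation between the preoperative RCSQ score and the outcome. It is an assumption and is shown as a range.

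**Step 1: reproduce the plan's figure.**
- Standard error = SD × √(2/n) = 45 × √(2/50) = 9.0 min.
- Noncentrality = 30/9.0 = 3.33, on 98 degrees of freedom.
- Power from the noncentral t distribution = 91.0% (normal approximation 91.5%). The stated figure holds.
- 95% CI half-width = 1.984 × 9.0 = 17.9 min.

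**Step 2: adjust for the baseline.** In a linear model with one covariate, the residual SD is 45 × √(1 − r²), on 97 degrees of freedom. The number of unadjusted completers giving the same precision is 100/(1 − r²).

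| r (assumed) | Residual SD, min | Reduction in SE | 95% CI half-width, min | Power | Equivalent total N |
|---|---|---|---|---|---|
| none (unadjusted) | 45.0 | – | 17.9 | 91.0% | 100 |
| 0.1 | 44.8 | 0.5% | 17.8 | 91.3% | 101 |
| 0.2 | 44.1 | 2.0% | 17.5 | 92.0% | 104 |
| 0.3 | 42.9 | 4.6% | 17.0 | 93.3% | 110 |
| 0.4 | 41.2 | 8.3% | 16.4 | 95.0% | 119 |

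Taking one more degree of freedom for the sedation stratum (96 instead of 97) leaves these powers and half-widths unchanged at the precision shown. Any further gain from the stratum itself is not counted.

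**Step 3: where in the range r is likely to lie.** The covariate is a subjective rating made before surgery; the outcome is EEG-scored sleep in the ICU after bypass and anesthesia. Importance of study says that sleep architecture is severely impaired in all patients under ICU conditions. Sleep in the ICU says that the cohort meets insomnia criteria regardless of any earlier diagnosis. Both point to a weak link between preoperative and ICU sleep, so to the upper rows of the table.

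**Step 4: RCSQ on its own baseline.** Here outcome and covariate come from the same instrument, so a useful correlation is more plausible. With r = 0.5 as an assumption, the variance falls by r² = 25%, and 100/(1 − 0.25) = 133, the precision of 33 more completers.

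**The case against.** The strongest reply is that nothing here is an error. Under randomization the unadjusted comparison is unbiased, its standard error already allows for chance baseline imbalance, and the planned power is met on the plan's own inputs. The prognostic value of preoperative RCSQ for EEG sleep is not shown anywhere in the documents. With r at 0.3 or below, the standard error falls by less than 5%. Completion is uncertain too: one night is requested and more only if possible, so patients will contribute different numbers of nights and some may contribute none, which would lower the usable r. All of this stands, and it is why the point is about efficiency and why the expected gain for WASO and TST is modest.

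A reader might infer that the baseline is not used at all. The documents do not support that: a preoperative RCSQ measure is among the factors for the exploratory TST models and the interaction step. That use is loosely defined, since the measure is called subjective TST while the five RCSQ items listed under Questionnaires/Assessments do not include total sleep time. A reader might also infer that the planned RCSQ comparison wastes precision. No such comparison is specified, so the gap there is a missing analysis.

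The reply does not remove two things. The RCSQ outcome still has no analysis. And the adjustment is nearly free. Its value would rise if the SD of 45 min, which is cited to a pooled analysis of elderly insomnia patients, proved low for the ICU. With an assumed SD of 55 min, the Step 2 calculation gives 77.1% unadjusted, 80.8% at r = 0.3 and 83.8% at r = 0.4.

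**Conclusion.** The point holds as one of efficiency and completeness. Preoperative RCSQ is available before randomization, is used only in exploratory effect-modifier models of TST, and does not adjust the WASO or TST comparisons. The RCSQ outcome has no specified comparison.

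For WASO, adjustment would move power from 91.0% to between 91.3% and 95.0% for r between 0.1 and 0.4, with the lower part of that range more likely. This rests on the plan's 30 min, SD 45 min and 50 per group, a linear relation, and a baseline available for essentially all patients. TST would gain by the same proportion at the same r, but the documents give no TST effect size or SD from which to state a power. The clearer benefit is for RCSQ adjusted for its own baseline.

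It would go too far to conclude that the primary test is invalid, that chance imbalance biases it, or that the sample size is inadequate. The documents support none of these.

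**What to change.** **Primary and secondary analyses.** Prespecify a linear model for WASO and for TST with treatment, the 420-minute sedation stratum and the mean preoperative RCSQ score. Define the score as the mean of the five items, averaged over the nights available, since the documents describe separate items and no total. Set a missing baseline to the overall mean, computed without reference to treatment arm. Report the adjusted difference in minutes with its 95% CI. Keep the rank-based test as a sensitivity analysis for non-normal data.

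**Study endpoints and Exploratory analyses.** List RCSQ for the sleep-trial night as an exploratory outcome and analyse it with the same model, its own preoperative score being the covariate. State when it is completed. The text gives no time point, and the procedures figure was not available for this review.

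**Variability in response to suvorexant treatment.** Use the same RCSQ definition there, so that the measure called subjective TST is identified.

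**Cost.** SAP wording before unblinding, one or two degrees of freedom, and the missing-baseline rule. No extra patients or assessments are needed if the questionnaire is already given after the sleep-trial night. If r is near zero, the gain for WASO will be little or nothing, and the loss is negligible.

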### B2. SIGNIFICANCE AND BACKGROUND FOR THE STUDY

#### **Importance of study**

Insomnia frequently occurs in patients admitted to an intensive care unit. ICU patients are exposed to circadian desynchronization phenomena similar to the experimental condition of a "constant routine", an established technique to assess human circadian rhythmicity and characterized by constant posture, temperature, dim light and noise, and feeding stimuli. Insomnia in the ICU can also be the consequence of a systemic stress response due to procedural pain and inflammation. In addition, centrally acting drugs given during anesthesia or for postoperative pain therapy could affect postoperative sleep in patients in the ICU [1]. Our data show that under these conditions, all patients demonstrate a severe impairment of sleep architecture [2]. Thus, it can be assumed that the majority of surgical ICU patients can be characterized as suffering from insomnia. As a consequence of the impaired sleep architecture, sleep promoting agents are frequently prescribed in ICU patients. In our hospital, patients who stay in the ICU for more than 48h often receive benzodiazepines (20%) and opioids (30%) during nighttime, which reduce REM sleep and have deliriogenic effects (see *Preliminary Data* below).

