#### Randomization and blinding

After postoperative extubation, eligible patients will be randomly allocated in a 1:1 ratio to receive either suvorexant 20 mg or placebo. If extubation is planned outside of research pharmacy hours, randomization and drug preparation will take place in coordination with research and hospital pharmacy in accordance with their policy. Randomization will be performed by computer-generated variable block size random allocation stratified by duration of perioperative anesthesia and sedation, using a cut-off value of 420 minutes of perioperative sedation (i.e. duration of anesthesia and postoperative sedation of equal to or over 420 minutes). The allocation sequence will be provided to the research pharmacy. To achieve blinding, the study drug and placebo will be delivered in the form of non-identifiable pills, containing either the active ingredient suvorexant, or lactose. Individual patients' drug bottles will be labeled with randomization numbers. Randomization number-specific codebreakers, prepared by the research pharmacy, will contain information about a patient's treatment allocation in a sealed envelope and will be kept in the patient's study record. If unblinding procedures are necessary for clinical reasons, the clinical team will be able to contact a member of the research team with access to the codebreaker at any time by pager or phone. The codebreaker envelope is only to be opened with PI approval as instructed on the envelope. The PI will immediately inform the research pharmacy and study team of any unblinding procedures. Delivery of research medication to the patient care area will take place per pharmacy guidelines. Disposal of any unused study medication will be done per pharmacy guidelines.

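### Randomization is stratified at 420 minutes of sedation but WASO and TST are compared without the stratum: the test is valid, and for WASO about 0 to 3 power points may be forgone

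*Combined protocol and SAP*

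**What the plan says.** In Section B3.A, Randomization and blinding, allocation is 1:1 in blocks of variable size and is "stratified by duration of perioperative anesthesia and sedation, using a cut-off value of 420 minutes of perioperative sedation". It takes place after extubation.

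In Section B3.B, Primary and secondary analyses, the comparison of WASO and TST is by intention to treat, and "we will analyze our data using a Student's t test, or Mann-Whitney-U test, as appropriate". No stratum term appears there or anywhere else for these two outcomes.

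The only regressions planned are exploratory. They examine the "association between each of the previously described potential confounders and TST during the night of the sleep trial". The candidate factors include measures related to the stratum ("duration of mechanical ventilation, total propofol dose since skin incision") but not the 420-minute stratum itself.

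Sample Size Justification rests on an unadjusted two-sample t-test: "We will consider a 30 minute difference in WASO as clinically meaningful, with a standard deviation (SD) of 45 minutes". It allows for loss as follows: "we plan to enroll up to 120 patients to achieve our desired sample size of 100 completed participants".

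**The concern.** Stratified allocation balances the stratum between arms, which removes between-stratum variation from the treatment difference. An unadjusted test still counts that variation as error. If long sedation goes with worse or better sleep, the estimated standard error exceeds the true one: the test rejects too seldom under the null, and the confidence interval is wider than it need be. If the stratum is unrelated to sleep, nothing is lost.

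What is at stake is a little precision that the design has already made available. There is also a reporting benefit. The section names tests but no effect estimate, whereas an adjusted mean difference with its interval would speak directly to the 30-minute difference on which the trial is sized.

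**Working it through.** **1. The plan's own figure.** Inputs from Sample Size Justification: difference 30, SD 45, 50 per group, two-sided 0.05.

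- Standard error = 45 × √(2/50) = 9.0 minutes.
- Noncentrality = 30/9.0 = 3.33, with 98 df.
- Power = 91.0% (normal approximation 91.5%). The stated figure above 90% is confirmed.

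**2. What the stratum could explain.** Let *g* be the gap in mean WASO between strata and *p* the share of patients in one stratum. Neither is in the documents; both are assumed. The share of variance explained is R² = g² × p(1−p)/45². For g = 9 and p = 0.5, this is 81 × 0.25/2025 = 1.0%. The gaps shown below as 20, 28 and 40 minutes correspond to R² of 5, 10 and 20%: 2 × 45 × √R² = 20.1, 28.5 and 40.2.

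**3. Closed-form check.** With the stratum in the model the residual SD is 45 × √(1−R²) on 97 df. Power is then 92.3, 93.6 and 95.8% at R² of 5, 10 and 20%. With perfect balance, the unadjusted type I error is 2 × [1 − Φ(1.96/√(1−R²))] = 4.4, 3.9 and 2.8%.

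**4. Simulation with loss.** 120 patients, 1:1 blocks of 4, 6 or 8 within stratum, 20 lost at random, 100 analysed, normal WASO with total SD 45, 40,000 runs per split. Block sizes, random loss and normality are assumptions. Results at a 50/50 split:

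| Gap (min) | R² (%) | Power, t-test (%) | Power, with stratum (%) | Gain (points) | Type I error, t-test (%) | 95% CI half-width, with stratum (min) |
|---|---|---|---|---|---|---|
| 0 | 0 | 90.9 | 90.9 | −0.1 | 5.07 | 17.84 |
| 9 | 1.0 | 91.0 | 91.1 | 0.1 | 4.95 | 17.75 |
| 15 | 2.8 | 91.1 | 91.6 | 0.5 | 4.78 | 17.59 |
| 20 | 5.0 | 91.3 | 92.2 | 0.9 | 4.58 | 17.39 |
| 28 | 10.0 | 91.7 | 93.4 | 1.7 | 4.18 | 16.93 |
| 40 | 20.0 | 92.5 | 95.7 | 3.2 | 3.33 | 15.96 |

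The unadjusted half-width is 17.8 minutes. Type I error with the stratum is 5.05%. Type I error of the t-test falls less than in step 3 because random loss disturbs the balance.

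The 28-minute row shows the mechanism. The true SD of the unadjusted difference is 8.68, but the mean estimated standard error is 8.98, and 8.98/8.68 is 3.5% too large.

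**5. Other settings.**

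- 80/20 split, same gaps: gains of −0.1, 0.0, 0.1, 0.4, 1.0 and 2.1 points.
- Rank tests, 50/50: van Elteren gains −0.3, −0.1, 0.4, 0.9, 1.8 and 3.6 points over Mann-Whitney.
- 100 randomized and none lost, gaps 0, 9, 20 and 40: gains of 0.0, 0.2, 0.8 and 2.6 points; unadjusted type I error 4.91, 4.78, 4.37 and 2.86%.

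**6. Skewed data.** Assumed gamma errors with shape 4 (skewness 1), total SD 45, a 30-minute shift, 50/50 split, 100 patients, 8,000 runs, gaps 0, 9, 20 and 40. Mann-Whitney has power 94.2, 94.3, 94.2 and 94.2%. Linear regression with the stratum has 91.3, 91.5, 92.3 and 95.5%. Forcing a linear model on skewed WASO would therefore lose 2.9, 2.8 and 1.9 points at the first three gaps.

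**The case against.** The strongest reply is that the plan contains no error. It is sized on a two-sample t-test and analysed with one, which is consistent; there are no extra false positives, and the claimed power holds. All of that stands.

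The benefit also rests wholly on assumed stratum gaps. The upper end needs a 40-minute gap, larger than the 30-minute treatment effect. That stands too, and it is why the result is given as a range that includes zero.

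A third objection concerns the remedy. Replacing the planned choice of test by linear regression in every case would be a separate change of method, and step 6 shows that with skewed data it could cost about as much as the best-case gain. It would also spill over: the Delirium paragraph of Exploratory analyses treats incidence, a binary outcome, by analogy with the primary analysis. Both criticisms are right, and the fix below is shaped by them.

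A reader might infer more than the documents support:

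- **That ignoring the stratum invalidates the test or inflates type I error.** The error goes the other way.
- **That the protocol treats sedation time as an established predictor of sleep.** Importance of study says only that "centrally acting drugs given during anesthesia or for postoperative pain therapy could affect postoperative sleep in patients in the ICU", and the related factors are left for exploration.
- **That the same power figure applies to TST.** No effect size or SD for TST is given.

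**Conclusion.** The omission is real and minor. For WASO at the design assumptions (30-minute difference, total SD 45, 100 analysed, normal data, 50/50 split), leaving out the stratum forgoes about 0 to 3 power points over assumed gaps of 0 to 40 minutes. The unadjusted test becomes conservative, with type I error falling from about 5% to about 3% at the top of that range. Below about 9 minutes there is nothing to gain.

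The range belongs to the full 30-minute effect, where power is already near its ceiling. If the true difference were 20 minutes (an assumption), simulated power without and with the stratum would be 59.9 versus 63.9% at R² 10%, and 59.9 versus 68.7% at R² 20%.

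The loss for TST cannot be sized. The change is worth making because it is nearly free; the planned analysis would be acceptable without it.

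**What to change.** In Section B3.B, Primary and secondary analyses, replace the last sentence with:

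> *WASO and TST will each be compared by linear regression with treatment and the randomization stratum as allocated (<420 / ≥420 min), or, where the Mann-Whitney test would have been used, by a van Elteren test stratified by the same factor; the stratum-adjusted mean difference with 95% CI will be reported.*

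In the Delirium paragraph of Exploratory analyses, state separately that delirium incidence is compared by a stratified method for a binary outcome, for example Cochran-Mantel-Haenszel, so that the reference back does not point to linear regression.

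The sample size text can stay, since the unadjusted t-test calculation does not overstate power.

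The cost is wording and one degree of freedom, with no extra patients or data: the stratum is known for every randomized patient because allocation follows extubation. If the stratum turns out not to be prognostic, the loss is about 0.1 point of power for the linear model and up to about 0.4 point for van Elteren.
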